Encouraging Mail Order Pharmacy Use to Improve Outcomes and Reduce Disparities

NCT02621476

Document date: 10/1/2020

Encouraging Mail Order Pharmacy Use to Improve Outcomes and Reduce Disparities

CLINICAL TRIAL PROTOCOL

Abbreviations:

CVD: cardiovascular disease

HPHC: Harvard Pilgrim Health Care Institute

IVR: automated telephone call (interactive voice response)

KP: Kaiser Permanente

KPNC: Kaiser Permanente Northern California

KPHI: Kaiser Permanente Center for Health Research, Hawaii

LDL: Low-density lipoprotein

PDC: Proportion of Days Covered

OBJECTIVE:

In this study, we seek to determine whether targeted, patient-centered interventions to encourage mail order pharmacy use will result in greater rates of mail order pharmacy use as well as improvements in medication adherence. We conducted a randomized encouragement trial to encourage use of the existing mail order pharmacy among diabetes patients with poor adherence to CVD risk factor medications who use only retail pharmacies and examined whether the intervention's impact differs across key subgroups. The specific aims of this clinical trial are to:

Aim 1: To test whether outreach strategies to encourage mail order pharmacy use will increase rates of mail order pharmacy use (Primary Outcome) in diabetes patients at high risk for poor health outcomes.

Aim 2: To examine whether encouraging the use of mail order pharmacy services to deliver cardiometabolic medications results in greater medication adherence, and to assess differences in the impact of the intervention across key subgroups.

BACKGROUND:

There is an urgent need for effective, sustainable interventions to improve diabetes medication adherence. Good medication adherence is associated with improved control of CVD risk factors, fewer hospitalizations, and lower mortality in patients with diabetes mellitus. However, only about 50-70% of patients with chronic conditions such as diabetes are adherent to their regular medications. In response to this problem, literally hundreds of interventions to improve adherence have been evaluated and published over the last 60 years. Traditional interventions almost always require substantial investments of personnel, time, and/or financial resources. However, they generally show only modest improvements in adherence, which dissipate completely once the active intervention phase concludes. Recent approaches such as medication therapy management are expensive to implement and limited to small subgroups of patients (e.g., Medicare Part D enrollees with multiple chronic diseases and multiple medications). These types of resource-intensive interventions will be challenging to disseminate and implement more widely and are unlikely to reach large numbers of adults with diabetes. Disparities in medication adherence are prevalent among patients with diabetes. The underlying reasons for these disparities in adherence are multifactorial, and include inability to afford prescribed medications, low health literacy and low health numeracy, low patient self-efficacy, inadequate patient-provider communication, and difficulty accessing pharmacies. Since poor medication adherence is linked to poor diabetes outcomes, improving adherence among minority and low-SES patients is critical in any effort to improve health care outcomes for these populations. There is only limited evidence that broadly targeted quality improvement efforts such as diabetes registries and care reminders impact disparities in diabetes care.

Evidence is growing that voluntary mail-order pharmacy use is linked to better adherence and outcomes. While the majority of efforts to improve adherence are focused on changing behavior at the individual level, recent studies have examined the role of pharmacy choice as a determinant of adherence. One recent multi- level analysis found that the between-pharmacy variation in medication adherence was significant and represents an independent pharmacy-level effect on adherence not explained by individual-level factors. This study also found that voluntary use of a mail-order pharmacy as compared to a retail pharmacy was associated with an 8-percentage point improvement in adherence to antidiabetic medications. Investigators on our study team have replicated this finding in several analyses using observational data for different chronic conditions, employing statistical approaches to mitigate selection bias. These studies show not only improved medication adherence with mail-order pharmacy use, but also lower LDL cholesterol among statin users and a decrease in racial disparities in adherence to antihypertensive medications. There is an urgent need for a well-designed, randomized trial to test strategies for improving mail order pharmacy use in diabetes patient at risk for poor health outcomes.

STUDY SETTING:

Research activities took place at the (3) locations listed below.

1. Kaiser Permanente Northern California (KPNC), Division of Research, Oakland, California
2. Kaiser Permanente Center for Health Research (KPHI), Honolulu, Hawaii
3. Harvard Pilgrim Health Care (HPHC) Institute, Boston, Massachusetts

STUDY DESIGN:

This study conducted a randomized encouragement trial to encourage use of the existing mail order pharmacy among diabetes patients with poor adherence to CVD risk factor medications who use only retail pharmacies. Subjects were randomized to (2) arms: 1) the intervention arm and 2) the usual care arm. Those randomized to the intervention arm, at all sites, received encouragement to use mail order pharmacy services by receiving an outreach letter, which includes information about the benefits of mail order pharmacy use, and information on how to enroll in mail order pharmacy services at their individual site. In addition, those randomized to the encouragement at KPNC and KPHI received an encouragement outreach email (secure message) and a pre-recorded phone message. Since phone and email contact with patients is not standard of care with HPHC, they received letter-only encouragement outreach. There was no outreach follow-up. Observational EHR data was used to examine the impact of the intervention on mail order use and medication adherence. Those patients randomized to the usual care arm did not receive any form of encouragement outreach from the study team.

STUDY POPULATION:

a. NUMBER OF SUBJECTS

63,012 total participants

b. INCLUSION AND EXCLUSION CRITERIA

Inclusion Criteria:

- Age 18 years or older
- Have a diagnosis of diabetes as indicated by EHR
- Have active health plan membership in the past 12 months
- Non-adherent (PDC <80%) to at least one oral CVD risk factor medications in the past 12 months
- Have no evidence of mail order pharmacy use to refill oral CVD risk factor medications.

Exclusion Criteria:

- Pregnancy or Dementia/Traumatic Brain Injury diagnosis in the past 12 months
- Hospitalized, in Skilled Nursing Facility, Hospice, or Home Health at the time of randomization

WAIVER OF INFORMED CONSENT and HIPPA PRIVACY RULE AUTHORIZATION:

A waiver of informed consent and HIPPA Privacy Rule Authorization was granted from KPNC IRB (IRB of record for this study) for participants in the study intervention. The only known risk is disclosure of confidential information. Safeguards were be put in place to prevent the loss of privacy and to prevent breaches of confidentiality. This study represented no more than minimal risk participants.

STUDY PROCEDURES:

Eligible patients were randomized into (2) arms: 1) an intervention arm and 2) a usual care arm. Those randomized to the intervention arm, at all sites, received encouragement to use existing mail order pharmacy services by receiving an outreach letter, which includes information about the benefits of mail order pharmacy use, and information on how to enroll in mail order pharmacy services at their individual site. The instructions on how to enroll in the existing mail order pharmacy services came directly from health plan operations materials. In addition, those randomized to the encouragement arm at KPNC and KPHI also received an encouragement outreach email (secure message) and pre-recorded phone message. Since phone and email contact with patients is not standard of care with HPHC, they received letter-only encouragement outreach. The letter and email outreach will be delivered only once. The Interactive Voice Response (IVR) system was programmed to make up to the IRB approved maximum attempts to contact eligible participants via phone to play the approved pre-recorded message: If a call is answered, the message begins. No PHI was disclosed in the outbound message. At the end of the call patients were given the opportunity to be transferred to their local mail order pharmacy phone line. Eligible members can hang up at any time and were not re-dialed. Those patients randomized to the usual care arm did not receive any outreach from the study team.

DATA ANALYSIS:

To examine the relationship of encouraging MOP use with MOP use and adherence, we estimated the differences in MOP use and CVD medication adherence at follow-up between the two arms using Chi-square tests in an intent-to-treat (ITT) analysis. Differences in the percentages of CVD drug fills delivered by mail were estimated using T-Test. To determine whether MOP use differed by race/ethnicity we calculated risk ratios using modified Poisson regression comparing the effect of treatment on outcomes within each group. We used Chi-square tests to compare the percent of patients with a hospitalization or emergency department visit during follow-up between the intervention and control arm and compared the number of primary care visits between arms using the Kruskal-Wallis test. Patients who died or who disenrolled from their health plan during follow-up were excluded from the analysis. In addition, those who did not have a CVD medication fill during the follow-up period were also excluded since we were unable to assess whether they used MOP. Sensitivity analysis was conducted to assess the impact of those without CVD medication fills during follow-up by including them in the analytic population as non-users of MOP at follow-up. All analyses were further stratified by site and results from both the KP sites were collapsed based on the similarity of study results in the two sites, and because their pharmacy distribution structure and health care systems were also similar in comparison to HPHC.

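### The overall adherence comparison (Aim 2) leaves out the screening PDC; adding it is an optional, cheap gain in precision whose size is unknown and ranges from negligible to modest

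*Combined protocol and SAP*

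**What the plan says.** Adherence is a stated aim: "Aim 2: To examine whether encouraging the use of mail order pharmacy services to deliver cardiometabolic medications results in greater medication adherence". The Data Analysis section gives the overall test, described as intent-to-treat: "we estimated the differences in MOP use and CVD medication adherence at follow-up between the two arms using Chi-square tests". It names no baseline covariate for this comparison or any other.

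Three other statements bear on the point.

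- An inclusion criterion under Study Population reads "Non-adherent (PDC <80%) to at least one oral CVD risk factor medications in the past 12 months". Eligibility could not be judged without computing a pre-randomisation PDC for each patient.
- A regression method is already in the plan, for race/ethnicity: "we calculated risk ratios using modified Poisson regression comparing the effect of treatment on outcomes within each group".
- Site is handled by separate results: "All analyses were further stratified by site". The two Kaiser Permanente sites are then combined. No site-adjusted pooled estimate is described.

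The documents do not define follow-up adherence or its cut-off. A binary outcome is inferred from the choice of a chi-square test.

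**The concern.** Past adherence usually predicts later adherence. When a predictive baseline value is already held, adjusting for it in a randomised comparison narrows the confidence interval at almost no cost.

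Precision has some value here because an encouragement design dilutes any effect on adherence: only patients whom the outreach moves to mail order can benefit through that route. As an illustration of scale, the Background cites an observational difference of 8 percentage points in adherence to antidiabetic drugs between mail-order and retail users. If the outreach raised mail-order use by an assumed 10 points, the difference between randomised arms would be 0.10 × 8 = 0.8 points. A shift that small is below what the unadjusted test detects with 80% power, even in a trial of this size.

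**Working it through.** **No figure to reproduce.** The documents give 63,012 participants but no power, alpha, target effect, adherence rate or allocation ratio.

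**Inputs from the documents.** 63,012 participants; PDC below 80% at entry; an unadjusted two-arm test of adherence.

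**Assumptions.** 1:1 allocation; two-sided 5% level; 20% of patients lost to the analysis exclusions, so 0.80 × 63,012 = 50,410 analysed; follow-up adherence cut at 80%; one drug; baseline and follow-up PDC linked through a bivariate normal with a given latent correlation; PDC distributed as Beta(2.2, 1).

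**Step 1: share of variance saved.** With linear adjustment the variance of the arm difference is multiplied by 1 − r², where r is the correlation of baseline PDC with binary follow-up adherence among eligible patients. The saving is r². Restricting entry to PDC below 80% and dichotomising the outcome both shrink r. Simulation with 2,000,000 draws gave:

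| Latent correlation | Saving r² | Adherent at follow-up | Patients equivalent (saving × 50,410) |
|---|---|---|---|
| 0.1 | 0.23% | 36.5% | 116 |
| 0.2 | 0.98% | 34.0% | 494 |
| 0.3 | 2.18% | 31.5% | 1,099 |
| 0.5 | 5.66% | 26.0% | 2,853 |
| 0.7 | 10.00% | 19.9% | 5,041 |
| 0.8 | 11.67% | 16.0% | 5,883 |

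**Step 2: sensitivity of the saving.**

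- Three other Beta shapes gave 0.9–1.0% at 0.2 and 11.4–12.4% at 0.8. The correlation drives the result; the shape hardly matters.
- A separate set-up, with a normal PDC and entry limited to the lowest 30%, 50% or 70%, gave about 0.7% to 9.8% for correlations of 0.2 to 0.7.
- Models fitted to simulated data with 50,410 patients gave adjusted-to-unadjusted variance ratios for the risk difference of 0.990 at 0.2 and 0.883 at 0.8. For the log risk ratio from modified Poisson regression they were 0.990 and 0.858.
- With PDC averaged over two or three drugs, and an assumed cross-drug latent correlation of 0.5, the saving was 1.3–1.4% at 0.2 and 17–21% at 0.8.

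**Step 3: effect on power.** Over the four shapes, savings near 12% went with 12–21% of patients adherent, so 20% adherent is a consistent choice.

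- Unadjusted SE = √(4p(1 − p)/N) = √(4 × 0.2 × 0.8/50,410) = 0.356 points.
- With a 12% saving, SE = 0.356 × √0.88 = 0.334 points. The confidence interval is 1 − √0.88 = 6% narrower.
- Difference detectable at 80% power = 2.80 × SE, which is 1.00 points unadjusted and 0.94 adjusted.
- Power = Φ(shift/SE − 1.96), plus the small opposite tail:

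| Assumed shift | Unadjusted | 1% saving | 12% saving |
|---|---|---|---|
| 0.4 points | 20.2% | 20.4% | 22.3% |
| 0.8 points | 61.2% | 61.7% | 66.8% |
| 1.2 points | 92.0% | 92.3% | 94.8% |
| 2 points | 100% | 100% | 100% |

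Over all possible shifts, the largest gain is about 0.4 points of power at a 1% saving and 5.6 at a 12% saving. The 0.8-point row therefore sits close to the peak.

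**The case against.** The best defence is that nothing is wrong. An unadjusted test of a binary outcome is a standard choice in a trial of 63,012, every size above is assumed, and at the low end nothing changes in practice. The remedy may also come late: the Data Analysis section is in the past tense and combines the Kaiser Permanente sites because their results were similar, so some results had evidently been seen. A covariate added then carries less weight. All of this stands, and it is why the point is graded optional.

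It does not remove the point. The covariate follows from the plan's own eligibility rule, the regression method is already in use, and reporting results by site does not adjust for baseline PDC.

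Four stronger readings are tempting and should be resisted.

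- A reader might infer that the overall comparison is unbiased apart from this loss of precision. The documents do not support that: "those who did not have a CVD medication fill during the follow-up period were also excluded". This exclusion is made after randomisation, outreach could affect who fills, and having no fill is itself a form of non-adherence. The stated sensitivity analysis puts these patients back only as non-users of mail order; none is described for adherence. Adjusting for baseline PDC does not address it.
- A reader might take 1% to 12% as firm limits. The saving is 0.2% at a latent correlation of 0.1, and it exceeds 12% in the strongest cases with several drugs.
- A reader might apply a 12% saving at 50% adherent. The model does not produce that pairing.
- A reader might extend the gain to the primary outcome. Patients enter under the criterion "Have no evidence of mail order pharmacy use to refill oral CVD risk factor medications", so mail-order use has no baseline value to adjust for.

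**Conclusion.** The point holds as a low-severity, optional improvement for Aim 2. A pre-randomisation PDC was computed for every patient, and the overall adherence test does not use it. The omission introduces no bias in itself; it costs precision.

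The cost cannot be fixed from the documents. It rests on the assumed correlation above all, and on one drug, an 80% follow-up cut, 1:1 allocation and 20% exclusions. On those terms it runs from negligible to modest, and only its upper end would move power by more than a few points. That the continuous PDC was retained is inferred, although it could be recomputed from the same fill records. No gain is claimed for site adjustment, which was not quantified.

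**What to change.** Keep the binary adherence outcome and the chi-square. Beside them, report the overall arm effect from a modified Poisson or risk-difference model with terms for arm, baseline PDC and site, robust standard errors and a 95% confidence interval. Compute baseline PDC by the same rule as the follow-up measure, for example the mean over the cardiovascular drugs held in the 12 months before randomisation, and state that rule. Such a mean can exceed 80%, because eligibility needs only one drug below the cut. Label the model post hoc if results were already known. In the report, do not describe the adherence comparison as unbiased while patients without a follow-up fill are left out.

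The cost is one added model and one covariate definition for patients on several drugs, with no new data collection. A post hoc model would carry less weight than a prespecified analysis.

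### Follow-up adherence is tested only as a category by chi-square; a comparison of mean PDC should be reported beside it, because a modest shift in PDC could be missed

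*Combined protocol and SAP*

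**What the plan says.** The Data Analysis section states: "we estimated the differences in MOP use and CVD medication adherence at follow-up between the two arms using Chi-square tests". The same sentence covers mail order use, which is naturally yes/no, and adherence, which is not. No other between-arm adherence analysis is described: no mean PDC, no change in PDC, no other comparison on a continuous scale. The next sentence of that section does use a t-test for another percentage, the share of CVD drug fills that came by mail.

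The abbreviation list gives "PDC: Proportion of Days Covered", and no other adherence measure is named. The only cutoff appears in the inclusion criteria: "Non-adherent (PDC <80%) to at least one oral CVD risk factor medications in the past 12 months". The document does not say which cutoff, time window or rule for combining several drugs defines adherence at follow-up.

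Adherence belongs to Aim 2. The primary outcome is in Aim 1, which asks whether outreach "will increase rates of mail order pharmacy use (Primary Outcome) in diabetes patients at high risk for poor health outcomes".

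**The concern.** A chi-square comparison sees only which side of a cutoff a patient falls on. Patients enter this trial because PDC is below 80% on at least one drug, so some can gain many covered days and still end below a cutoff. If 80% were also used at follow-up, a patient moving from 30% to 70% would score the same as one who did not change, while a move from 78% to 81% would count as a success.

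This matters because the intervention is light: a letter at all sites, a secure message and recorded call at the two Kaiser sites only, and no outreach follow-up. Only some patients will change pharmacy because of it, so the average between-arm difference in adherence is diluted. A null Aim 2 result could then reflect the cutoff rather than no effect on adherence. The analysis also gives no estimate in PDC points or days covered.

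**Working it through.** The document gives no power calculation, so there is no planned figure to reproduce. The check asks how much a binary cut costs relative to a comparison of means.

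**Inputs from the document**
- Sample size: "63,012 total participants" (Study Population). This is a count with no stated justification.
- Two arms (Study Design). No allocation ratio is given.
- The only adherence effect size is in the Background: voluntary mail order use was "associated with an 8-percentage point improvement in adherence to antidiabetic medications". It is observational and is not a design assumption.

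**Assumed, because not stated**
- Two-sided alpha 0.05; 1:1 allocation, so n = 63,012 / 2 = 31,506 per arm, with no exclusions.
- SD of PDC 25 points; 35% adherent at follow-up (20-50% for the efficiency figures).
- The 8 points read as PDC points among patients who move to mail order; uptake raised by 2, 5 or 10 percentage points.

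**Step 1: information kept by the cut, under a normal shift.** With a proportion p adherent, c = z(1 − p) and φ the normal density, efficiency relative to the mean is φ(c)² / [p(1 − p)].

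| p adherent | Efficiency | Loss |
|---|---|---|
| 50% | 0.637 | 36% |
| 40% | 0.622 | 38% |
| 30% | 0.576 | 42% |
| 20% | 0.490 | 51% |

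The smallest loss under this model is 1 − 2/π = 36%, at p = 50%.

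**Step 2: what that means for power.** The intention-to-treat shift is δ = 8 × uptake.
- Mean PDC: z = δ / (SD × √(2/n)). The denominator is 25 × √(2/31,506) = 0.199.
- Binary: z = (δ/SD) × φ(c) / √(2p(1 − p)/n). With p = 0.35, φ(c) = 0.370 and the denominator is √(2 × 0.2275/31,506) = 0.0038.

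For 5 points of uptake, δ = 8 × 0.05 = 0.40. The mean gives z = 0.40 / 0.199 = 2.01. The binary outcome gives z = 0.016 × 0.370 / 0.0038 = 1.56.

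| Extra uptake | Shift (PDC points) | Power, means | Power, binary |
|---|---|---|---|
| 2 points | 0.16 | 13% | 10% |
| 5 points | 0.40 | 52% | 34% |
| 10 points | 0.80 | 98% | 88% |

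The SD matters. At 5 points of uptake, with 30-50% adherent, SD 20 gives 71% versus 48-52%, and SD 30 gives 39% versus 25-27%.

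**Step 3: does the loss survive when PDC is bounded and skewed?** PDC was simulated from six beta distributions with an assumed 80% cutoff, under five patterns of effect. Efficiency of the chi-square relative to the t-test (above 1 favours the chi-square):

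| Pattern of effect | Relative efficiency |
|---|---|
| Everyone gains 3 points | 0.46-0.62 |
| Everyone closes 10% of the gap to 100% | 0.10-0.37 |
| Only patients below 60% gain, by 10 points | 0 |
| A random 3% jump to 95% | 0.89-1.44 |
| Only patients at 60-80% gain, crossing the cutoff | above 3 |

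The size of the loss, and even its direction, depends on who moves and how far.

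**The case against.** A reader might infer that at least a third of the information is always lost. The documents do not support that. The 36% minimum belongs to a normal shift affecting everyone. In an encouragement trial a few patients may move a long way, and Step 3 shows little or no loss, or a gain, in that case. This objection stands in full.

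A reader might also take 80% as the follow-up cutoff. It is stated only for entry. That follow-up adherence is a cut of PDC is a reasonable inference, but not a written one, and a mean-PDC analysis needs the same missing definition. This stands too. It does not remove the point, because a chi-square requires categories whatever the cutoff.

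The power illustration rests on several assumed figures and on all 63,012 patients, although deaths, disenrolments and patients without a CVD fill are excluded. The 8 points concern antidiabetic drugs and may not be mean PDC at all. The illustration is therefore indicative only.

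The consequence is also bounded. Adherence is not the primary outcome, percent adherent is consistent with the protocol's own threshold framing, and at 1:1 the chi-square detects a difference of about 1.0-1.1 percentage points in the adherent proportion with 80% power (control rates of 30-50%). Still, effects diluted below 1 PDC point are plausible here, so a large sample does not make the loss harmless.

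Finally, one could argue for replacing the binary endpoint with mean PDC. The document is dated October 2020, is largely in the past tense, and says the Kaiser sites were pooled partly because their results were similar. Results had been seen by then, so swapping the endpoint is not clearly defensible. Adding an analysis, labelled as such, is.

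**Conclusion.** The point holds in a limited form. Follow-up adherence is compared by a categorical test only, no continuous comparison is described, and gains that stop short of the cutoff do not register. If the effect is a modest shift in PDC, roughly a third to a half of the information goes (36-51% under a normal shift with 20-50% adherent). Under other patterns the loss can be larger or absent. The illustrative power figures depend on the assumed allocation, SD, adherent proportion, uptake and reading of the 8 points.

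Because the pattern of change cannot be known in advance, reporting both scales is sounder than relying on either alone. The primary outcome is unaffected.

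**What to change.** In the Data Analysis section, add the between-arm difference in mean follow-up PDC (0-100%) with a 95% CI, by t-test or by linear regression with robust standard errors. Keep the existing chi-square on the adherent proportion beside it. Use one PDC definition for both, and write it down: the follow-up window, how several drugs are combined, and the cutoff for the binary version. Label the continuous comparison as supplementary if it is added after results were seen.

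The cost is a few lines of wording, one extra model and a second adherence result to report. If the binary outcome was derived from PDC, the values already exist. Mean PDC is less familiar to health-plan readers than percent adherent, which is a further reason to show both.

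### Does this encouragement trial need a complier (instrumental-variable) analysis to link the adherence difference to mail-order uptake?

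*Combined protocol and SAP*

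**What the plan says.** The Objective section states Aim 2 as follows: "To examine whether encouraging the use of mail order pharmacy services to deliver cardiometabolic medications results in greater medication adherence". The Study Design section describes the trial in the same terms: "This study conducted a randomized encouragement trial to encourage use of the existing mail order pharmacy". The number of subjects is "63,012 total participants".

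The Data Analysis section opens by giving its purpose as relating encouragement to both mail-order use and adherence. It then compares the two outcomes between arms "using Chi-square tests in an intent-to-treat (ITT) analysis" and adds a t-test on the percentage of CVD fills delivered by mail. All analyses are also stratified by site, with the two Kaiser sites combined. There is no instrumental-variable or complier-average analysis in this section or elsewhere in the document.

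The Background section cites an observational finding that voluntary mail-order use "was associated with an 8-percentage point improvement in adherence to antidiabetic medications". It closes with the need the trial is meant to meet: "There is an urgent need for a well-designed, randomized trial to test strategies for improving mail order pharmacy use".

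**The concern.** In an encouragement design, assignment moves only some patients to mail order, so any effect of mail order on adherence is diluted in the comparison by arm. The Background gives readers a figure for mail order itself, and the outreach was light: one letter everywhere, with one secure message and a recorded call added at the Kaiser sites only. If few patients switched, a null adherence result could be misread as evidence that mail order does not help. The plan measures uptake and adherence but never combines them, and it does not state the assumptions under which they could be combined. A statistician who knows encouragement designs would look for a complier estimate and not find one.

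**Working it through.** **Step 1: question against analysis.** Aim 2 concerns the effect of encouraging mail order. The planned estimate is the difference in adherence between those assigned and those not assigned to encouragement. The two match. The need stated at the end of the Background is also about strategies to increase use. No section announces a conclusion about mail order as such, and the opening of the Data Analysis section already frames the results as effects of encouragement.

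**Step 2: how much dilution there could be.** The documents give no power calculation, uptake difference, allocation ratio or control-arm adherence, so there is no figure to reproduce. Assumptions: 1:1 allocation (31,506 per arm), everyone analysed, two-sided 5%, 50% adherent, and 8 points gained per patient moved. The 8 points are observational, relate to antidiabetic drugs and are on an unstated scale, so they only illustrate.

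- SE of the adherence difference = sqrt(2 × 0.5 × 0.5 / 31,506) = 0.398 points
- 95% half-width = 1.96 × 0.398 = 0.78 points
- Expected intent-to-treat difference = 8 × uptake difference d (d as a proportion)
- Complier half-width ≈ 0.78 / d, treating uptake as known

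| Uptake difference | Expected adherence difference | Power | Complier half-width |
|---|---|---|---|
| 5 points | 0.40 | 17% | 15.6 |
| 10 points | 0.80 | 52% | 7.8 |
| 15 points | 1.20 | 85% | 5.2 |

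For 80% power, the detectable difference is 2.80 × 0.398 = 1.116 points, which needs an uptake difference of 1.116 / 0.08 = 13.95 points. With 30% adherent it is 12.8 points. With 80% of patients analysed, the range is 14.3 to 15.6. If the 8 points were mean PDC with an SD of 20 to 30 points, it would be 5.6 to 8.4 with all analysed. So the dilution could be large, but whether it is depends on inputs that the documents do not supply.

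**Step 3: what the complier estimate would add.** Its last column is the constant 0.78 divided by d. Treating uptake as known, the scaled interval excludes zero exactly when the unscaled one does, so it adds no power. Nor is it needed to tell an uninformative null from an informative one. With an observed adherence difference near zero, the data are compatible with an 8-point effect when 8 × d is below 0.78, that is, when d is below 0.78 / 8 = 0.098, or about 9.8 points. A reader can make that comparison from the uptake difference, the adherence difference and the counts, all of which follow from the planned analyses, by site as well.

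**Step 4: what it would cost in assumptions.** The estimate requires outreach to affect adherence only through mail-order use. At the Kaiser sites, patients in the encouragement arm "also received an encouragement outreach email (secure message) and pre-recorded phone message" on top of the letter, and all were non-adherent at entry, so a reminder effect is plausible. A direct effect r biases the complier estimate by r / d. With r = 0.2 points, the bias is 0.2 / 0.05 = 4 points at 5-point uptake and 0.2 / 0.10 = 2 points at 10. Bias and imprecision are both worst at low uptake, where the analysis was supposed to help. Coding exposure as any mailed fill also assumes that outreach does not change the number of mailed fills among patients who would use mail order anyway. The plan itself measures the percentage of fills by mail, so intensity can vary.

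**The case for a change.** The best case for a defect is that the absence is real, the data are in hand, and the trial calls itself an encouragement trial and cites evidence on mail order itself. A reader dividing two reported differences gets a ratio without a proper interval, covariate adjustment or stated assumptions. The instrument would not be weak overall: with assumed control-arm use of 5% to 10%, a 3-point uptake difference gives F of about 234 to 140. A labelled supplementary estimate would guard against misreading a null result.

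The absence and the conditional arithmetic stand. A proper interval would be tidier than a reader's division. None of this shows that a planned result is wrong or that a planned conclusion goes beyond its analysis. An encouragement design permits a complier analysis but does not oblige one, and with an exclusion restriction this doubtful, reasonable statisticians would differ on including it.

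Overall instrument strength does not carry over to each site group. If HPHC had 2,000 patients (an assumption, split 1:1), the same 3-point difference would give F of only about 4 to 7.

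The analysis would also need rules for adherence in patients without fills, and for those covered by the statement "Patients who died or who disenrolled from their health plan during follow-up were excluded from the analysis". Whether those exclusions suit the intent-to-treat label is a separate matter that a complier estimate would not settle.

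**Conclusion.** The concern does not hold. The planned comparison by arm answers Aim 2 as written, and the plan already frames its results as effects of encouragement. The complier analysis would target a further quantity that neither aim asks for. Treating uptake as known, its interval is the planned adherence interval divided by the planned uptake difference.

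The interpretive limit is genuine but conditional. Power would be 17% at a 5-point uptake difference and 85% at 15 points, assuming 1:1 allocation, 63,012 analysed, 50% adherent and 8 points per patient moved, and the documents do not show which case applies. At 5-point uptake, the added estimate would have a half-width of about 16 points and could carry 4 points of bias from a reminder effect of 0.2 points. Adding it is a matter of preference. Leaving it out is neither an error nor a clear shortfall.
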